AXIS Protocol

Cover Page

NCT01541748

**Axis Allograft Dermis for female Pelvic Floor Repair: a Prospective Post Market
Study**

Most recent version 24Oct2011

Axis™ Allograft Dermis for Female Pelvic Floor Repair: a Prospective Post Market Study

Clinical Investigational Plan (CIP)

Investigational Plan #: CP009SU

This confidential document is the property of Coloplast Corp. No unpublished information contained herein may be disclosed without written approval of Coloplast Corp.

Signature page

SPONSOR	INVESTIGATOR
Coloplast Corp. [name] USA [contact]	Name Address Postal code and city Country Telephone number:
APPROVER	
	Name and title of the Investigator
Date	Date
Date	
Date	

Table of Contents

Signature page 2

1 Protocol Summary 4

2 Background 4

3 Product Description 6

4 Study Purpose and Design 6

5 Objectives 6

6 Study Population 7

7 Enrollment 7

8 Procedures 8

9 Study Product 10

10 Protocol Deviations 11

11 Adverse Events 11

12 Withdrawal / Study Exit 13

13 Electronic Case Report Forms (eCRFs) 13

14 Statistical Methods 13

15 Data Quality Assurance 14

16 Regulations and Guidances 15

17 Publication 16

18 Records and Retention 16

19 [REDACTED] 18

Appendix A: [REDACTED] 20

Attachment 1: [REDACTED] 22

Appendix B: Patient Questionnaires 24

1 Protocol Summary

Title	Axis™ Allograft Dermis for female pelvic organ prolapse repair: a post market study
Sponsor	Coloplast Corp. [name]
Product	Axis Allograft Dermis
Study Design	A prospective, single arm, multi-center, post market study of the efficacy of Axis™ Allograft Dermis for anterior, posterior or combined female pelvic floor repair.
Primary Objective	POP-Q Stage improvement from baseline at 1 year post operatively, categorized as cure, improved or failed.
Secondary Objective	POP-Q Stage at 6 weeks, 6 months, 2 year, and 3 year follow-up 
Brief Entrance Criteria	
Diagnosed with clinically significant pelvic organ prolapse of Stage 2 or higher as determined by POP-Q prolapse grading requiring surgical intervention in the anterior, posterior or combined (anterior and posterior) compartment.
 
Must be willing and able to complete all follow-up visits and procedures indicated in this protocol
 
No prior prolapse implant or procedure
 
No concurrent surgical treatment of prolapse using anything other than Axis
 
No history of previous pelvic radiation
 
No severe urogenital atrophy
 
No immunosuppression and/or current systemic steroid use
 
No contraindication to the surgical procedure

Visit Schedule	Study visits will take place at baseline, implant/hospitalization, 6 weeks, 6 months, 1 year, 2 years, and 3 years post operatively.
Scope	This study will target enrollment of 70 to 100 subjects at 5 to 10 US investigative sites.

2 Background

A woman's organs can shift position overtime as she ages or, in some cases, it can happen without any notice or warning. Pregnancy, childbirth, genetic predisposition, menopause, prior pelvic surgery, connective tissue disorders, and factors associated with elevated intra-abdominal pressure such as obesity, chronic constipation, and excessive straining can stretch and weaken the muscles that support the pelvic organs. A sheet of muscles, ligaments, and connective tissue called the pelvic floor supports

the uterus, small intestine, colon and bladder. If pelvic floor muscles are weak, the organs may drop, protruding into the vagina causing a Pelvic Organ Prolapsed (POP).

This condition affects millions of women and with the advancing age of the U.S. population, health care providers are likely to encounter women with pelvic organ prolapse with greater frequency. A woman's lifetime risk (up to the age of 80 years) for undergoing prolapse surgery has been estimated at 11 percent¹. Approximately 200,000 inpatient procedures for prolapse are performed annually in the United States alone².

Pelvic organ prolapse can be categorized into four areas:

Cystocele or anterior prolapse: When the vaginal wall weakens and allows the bladder to protrude into the vagina from above.

Vaginal vault or uterine prolapse: When the top of the vagina loses its support and drops.

Rectocele or posterior prolapse: When the back of the vagina weakens and allows the rectum to protrude into the vagina.

Enterocoele: When the small intestine drops and protrudes into the vagina. This usually occurs in conjunction with one or more of the other types of prolapse listed above.

Depending on the severity and stage of prolapse, many women do not need treatment. Some women find that their symptoms are relieved through special pelvic muscle exercises call Kegel Exercises, which are used to strengthen the muscles that surround the opening of the urethra, vagina, and rectum. Making dietary changes, maintaining a healthy weight, not smoking, and avoiding heavy lifting and straining also help to relieve symptoms. Medication is available to help treat urinary and bowel symptoms of POP. Further, a device called a pessary can be inserted into the vagina to support the pelvic organs. For women who can be fitted properly and whose pelvic organ support can be maintained with a pessary, this form of treatment has a high probability of success.

[REDACTED]

[REDACTED]

3 Product Description

Coloplast's Axis™ Allograft Dermis consists of [REDACTED], preserved human collagen. [REDACTED]

4 Study Purpose and Design

This study is a prospective, single arm, multi-center, post-market study to evaluate the efficacy of Axis™ Allograft Dermis used for anterior, posterior or combined (anterior and posterior) pelvic organ prolapse repair. Target enrollment is 70-100 subjects enrolled at 5 to 10 investigational sites in the United States. [REDACTED]

5 Objectives

5.1 Primary Objective

The primary objective of this study is to evaluate efficacy of the Axis Dermis graft used for soft tissue repair, replacement, reconstruction, or augmentations in the correction of POP as assessed by POP-Q Stage improvement based upon an objective grading of prolapse of the anterior, posterior or combined anterior and posterior (assessed individually) compartment(s) compared between baseline and one year. Grading of the prolapse will be categorized as follows:

Cured: POP-Q Stage reduced to 0 or 1, or improved by 2 stages from baseline

Improved: POP-Q Stage > 1, but improved by 1 stage from baseline

Failed: POP-Q Stage stayed the same or increased in severity from baseline

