5.2 Secondary Objectives

Secondary objectives will assess POP-Q Stage and patient satisfaction at 6 weeks, 6 months, 2 years, and 3 years post implant, as follows:

Change in prolapse stage from baseline as determined objectively by POP-Q prolapse grading at 6 weeks, 6 months, 2 year, and 3 year follow-ups. Change in patient satisfaction from baseline and quality of life measured through validated questionnaires (PDFI-20 and PFIQ-7)⁶

Change in patient sexual satisfaction from baseline measured through a validated questionnaire (PISQ-12)⁷

Summary of Patient Global Impression of Improvement (PGI-I) for urogenital prolapse⁹ results

Summary of The Institute for Female Pelvic Medicine & Reconstructive Surgery Surgical Satisfaction Questionnaire (SSQ-8) results¹⁰

Change in Pelvic and Sexual Health Institute Visual Analog Scale (VAS)¹¹ results

Surgical revision rate of the index prolapse(s)

Summary of all mild, moderate, and serious product and/or procedure related adverse events

6 Study Population

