8.5 Follow-Up Visits

8.6 Revision Procedure

If during the follow up period a subject requires urogynecological surgery (i.e. additional or revision POP repair, mid-urethral sling, hysterectomy, etc.), complete the Revision Form. If a revision procedure is performed as the result of an adverse event (e.g. infection, rejection, pain), complete the Adverse Event form in addition to the Revision form.

9 Study Product

All investigative sites will be required to maintain an adequate stock of Axis Dermis. The lot number and size of each product used will be recorded on the Procedure Form.

10 Protocol Deviations

A protocol deviation is defined as an event where the clinical investigator or site personnel did not conduct the study according to the clinical investigational plan or the investigator agreement. All protocol deviations must be documented on a Study Deviation Case Report Form.

Reporting of protocol deviations should comply with local IRB policies and/or local laws.

11 Adverse Events

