14.1 Sample Size

In the absence of predefined hypotheses, the desired sample size is based on the precision of estimates and half-widths of confidence intervals. The target enrollment cohort of 70 to 100 will provide between 60 and 85 evaluable subjects at month 12 [REDACTED]

Table 3 Sample Size Calculations

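### On the visible text, a compartment re-operated for prolapse before the 1-year visit and then at Stage 0-1 counts as Cured, although that stage does not measure the index Axis repair

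*Combined protocol and SAP*

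**What the plan says.** - **Outcome.** The Protocol Summary gives the primary objective as "POP-Q Stage improvement from baseline at 1 year post operatively, categorized as cure, improved or failed". Section 5.1 sets the categories. The top one is "Cured: POP-Q Stage reduced to 0 or 1, or improved by 2 stages from baseline" and the bottom one is "Failed: POP-Q Stage stayed the same or increased in severity from baseline". The comparison is by compartment: "combined anterior and posterior (assessed individually) compartment(s) compared between baseline and one year". Neither place mentions surgery between baseline and one year. Section 5.1 shows no redaction.
- **Repeat surgery.** Section 8.6 provides for the case where "a subject requires urogynecological surgery (i.e. additional or revision POP repair, mid-urethral sling, hysterectomy, etc.), complete the Revision Form". An Adverse Event form is added if the revision results from an adverse event. Neither study exit nor a change of outcome category follows.
- **Population.** Section 14.2 retains every woman who was enrolled and has follow-up in the primary analyses. It adds a separate tabulation that sets women who were revised and received a non-Axis product against women who received nothing but Axis.
- **Revision as an outcome.** Section 5.2 lists the rate of surgical revision of the index prolapse as a secondary objective.
- **Size.** Under section 14.1, "the desired sample size is based on the precision of estimates and half-widths of confidence intervals", and an enrolment of 70 to 100 "will provide between 60 and 85 evaluable subjects at month 12". There are no predefined hypotheses.
- **Not visible.** The opening of 14.2, the end of the efficacy paragraph in 14, part of 14.1 and the contents of Table 3.

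**The concern.** The stated aim in 5.1 is the efficacy of the Axis graft in correcting prolapse. If a repair fails, the compartment is operated on again and the 1-year examination then finds Stage 0 or 1, that stage is the result of the second operation. The printed definition still reads it as a cure. The women in whom the first repair did worst can thus enter the primary result as successes.

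Relative to counting such compartments as Failed, the stage-only rule can only raise the cure rate. The study exists to estimate that rate with stated precision and to set it beside published results for other products, so readers need to know which quantity is being reported. If the choice is left until the data are in, either answer is open to challenge.

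**Working it through.** **1. The plan's own figure.** Evaluable numbers are 60 to 85 from 70 to 100 enrolled. No attrition rate is visible. Back-solving gives 1 − 60/70 = 14.3% and 1 − 85/100 = 15.0%. A single 15% gives 70 × 0.85 = 59.5 and 100 × 0.85 = 85.0. The figures are consistent with each other, and I use n = 60 and n = 85 below.

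**2. The rule applied to one case.** Take baseline Stage 3, recurrence at 6 months, repeat repair of the same compartment, and Stage 1 at one year.
- Cured (5.1): the stage has been reduced to 0 or 1, so the condition is met.
- Failed (5.1): the stage is neither unchanged nor worse, so the condition is not met.
- Primary analyses (14.2): she was enrolled and followed, so she is included.

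She counts as a cure.

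**3. Whether another provision changes that.**
- The revision rate in 5.2 is a separate outcome and alters no classification.
- The tabulation in 14.2 is additional and recodes no one. It splits on receipt of a non-Axis product, so by its wording a woman re-repaired with Axis, or with no product, stays in the Axis-only group and can be Cured there too.

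**4. Points per case.** With one treated compartment per woman, each case adds 100/n: 100/60 = 1.7 points and 100/85 = 1.2 points. Section 5.1 assesses compartments separately, so the true denominator may differ. If every woman had both compartments repaired and they were pooled, one compartment would add 100/120 = 0.8 or 100/170 = 0.6 points. If women split evenly between two single-compartment denominators, it would add 100/30 = 3.3 or 100/42.5 = 2.4 points.

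**5. Total shift.** Shift = (proportion re-repaired before month 12) × (proportion of those then Cured). Both inputs are assumptions.

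| Re-repaired | 70% then Cured | 100% then Cured |
|---|---|---|
| 2% | 1.4 points | 2.0 points |
| 5% | 3.5 points | 5.0 points |
| 10% | 7.0 points | 10.0 points |

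In counts, starting from an assumed cure rate near 75% without re-repaired women:
- n = 60: 45/60 = 75.0%. With 1, 3 or 6 re-repaired women read as Cured it becomes 46/60 = 76.7%, 48/60 = 80.0% or 51/60 = 85.0%.
- n = 85: 64/85 = 75.3%. With 2, 4 or 8 it becomes 66/85 = 77.6%, 68/85 = 80.0% or 72/85 = 84.7%.

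**6. Scale against precision.** The confidence level and interval method are not visible, so I assume a two-sided 95% normal-approximation interval at a 75% cure rate. The half-width is 1.96 × √(0.75 × 0.25/n), which is 11.0 points at n = 60 and 9.2 points at n = 85. As a share of the half-width:
- 2% re-repaired: 1.4/11.0 = 0.13 to 2.0/9.2 = 0.22
- 5% re-repaired: 3.5/11.0 = 0.32 to 5.0/9.2 = 0.54
- 10% re-repaired: 7.0/11.0 = 0.64 to 10.0/9.2 = 1.09

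**The case against.** **A rule may already exist.** The redacted opening of 14.2 is where one would expect it, and redacted text is not missing from the plan. This stands. A reader might infer that the plan has no rule for re-operated women, but the documents do not support that. They support only that the visible definition, which is complete as printed, yields Cured and points to no exception.

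**The plan already deals with revision.** Re-operations are recorded, a revision rate is reported, and women revised with another product are tabulated separately. This stands in part: a careful reader would see that revisions took place. The primary rate is unchanged all the same, and re-repairs with Axis or without a product are not separated out.

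**Observed stage in everyone followed is a legitimate quantity.** It is coherent as a description of where women are at one year, whatever happened in between. It is less apt for an objective framed as the efficacy of the graft. This supports reporting both definitions. It gives no reason to exclude re-operated women; keeping them in is right.

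**The size is hypothetical.** This stands. No re-operation rate, cure rate or cure rate after revision appears in the documents.

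Two further inferences are tempting and unsupported:
- *The confidence interval is invalid.* It remains valid for the stage-only rate. It misses only if judged against the other definition, and by how much depends on the assumed shift. With no hypotheses planned, no test is affected.
- *The literature comparison favours Axis.* That depends on how each comparator defined cure, which the documents do not show.

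**Conclusion.** The point holds on the visible text and is worth fixing before analysis. Sections 5.1, 8.6 and 14.2 read together make a compartment re-repaired before one year and then at Stage 0-1 a cure, and no visible provision reverses that. The direction is certain relative to counting such compartments as Failed; the size is not known. On the assumptions above, the effect is small beside the sampling error at 2% re-repaired, about a third to just over half of a half-width at 5%, and about two thirds to slightly more than a whole one at 10%. Confidence is medium, because the redacted text of section 14 could already settle the matter. Revisions for reasons other than prolapse, such as infection or pain, are outside this point.

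**What to change.** This concerns the analysis only and leaves the management of the women untouched.

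1. Check the redacted text of section 14. If it already says how a re-repaired compartment is classified, add a cross-reference in 5.1.
2. If it does not, state in 5.1 and 14.2 before analysis: for the 1-year efficacy result, a treated compartment that had repeat surgery for prolapse in that compartment before the 1-year assessment is classified as Failed, whatever product was used and whatever its later stage. Report the stage-only classification beside it.
3. Apply the same pair of definitions at the later visits, with surgery counted up to the visit in question.
4. For each literature comparison, use whichever definition matches the comparator.

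The cost is a few sentences and one extra table, with no added women or visits. The Revision Form, which is not shown, must record date, compartment and reason, so a field may have to be added. The reported cure rate may be slightly less favourable.

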6.3 Inclusion Criteria

Patients must meet all of the following criteria to be included in the study:

1. Adult female at least 18 years of age.
2. Willing and able to provide written informed consent.
3. Confirmed pelvic organ prolapse (POP) of Stage 2 or higher as determined by POP-Q prolapse grading requiring surgical intervention in the anterior, posterior or combined (anterior and posterior) compartment.
4. Willing and able to complete all follow-up visits and procedures indicated in this protocol.

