6.4 Exclusion Criteria

Patients who meet any of the following criteria are excluded from entry into the study:

1. Concurrent surgical treatment of pelvic organ prolapse using anything other than the Axis Dermis. [Note: concurrent mid-urethral sling placement for treatment of stress urinary incontinence is allowed].
2. Confirmed Stage 2 or higher prolapse as determined by POP-Q prolapse grading for a compartment that is **not** being repaired in the same procedure. (Concurrent POP-Q Stage 1 repair is at the physician's discretion.)
3. Previous pelvic organ prolapse repair using biologic, or synthetic grafts. [Note: previous mid-urethral sling for treatment of stress urinary incontinence is allowed]
4. Pregnant or a desire to become pregnant in the future.
5. Previous radiation or other treatments for cancer in the pelvic area.
6. Severe urogenital atrophy.
7. Immunosuppression and/or current systemic steroid user.
8. Any contraindication to the surgical procedure.

7 Enrollment

[figure not shown]
After it has been determined that a potential study participant meets the entrance criteria and prior to data being collected, an informed consent must be obtained. There is no formal screening process outside of standard of care procedures required to determine participant eligibility. [REDACTED]

[REDACTED] Once it is determined the participant meets all of the inclusion and none of the exclusion criteria, they are considered enrolled in the study. When they are enrolled they will receive a subject number.

8 Procedures

Clinical data will be collected at baseline, implant, 6 weeks, 6 months, 1 year, 2 years, and 3 years post-operatively. The Data Collection Schedule below provides an outline of what clinical and participant data is collected at each visit (Table 1).

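### The two-stage branch of Cured in 5.1 has no limit on the final stage, so a compartment that goes from Stage 4 to Stage 2 is counted as cured

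*Combined protocol and SAP*

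**What the plan says.** Section 5.1 sorts each repaired compartment into one of three categories at one year:

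- The best category is worded "Cured: POP-Q Stage reduced to 0 or 1, or improved by 2 stages from baseline", with two alternative routes into it.
- The middle category is worded "Improved: POP-Q Stage > 1, but improved by 1 stage from baseline", so it covers a single-stage gain only.
- The worst category is worded "Failed: POP-Q Stage stayed the same or increased in severity from baseline", which takes in every compartment without a gain.

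Compartments in a combined repair are classified separately: "combined anterior and posterior (assessed individually) compartment(s) compared between baseline and one year".

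Stage 2 is the threshold for prolapse elsewhere in the document. Inclusion criterion 3 in 6.3 asks for "Confirmed pelvic organ prolapse (POP) of Stage 2 or higher as determined by POP-Q prolapse grading requiring surgical intervention". The Protocol Summary has "Diagnosed with clinically significant pelvic organ prolapse of Stage 2 or higher". Exclusion criterion 2 in 6.4 rules out a woman who has "Confirmed Stage 2 or higher prolapse as determined by POP-Q prolapse grading for a compartment that is" left out of the repair. There is no upper limit on baseline stage, so Stage 4 is eligible. Exclusion criterion 2 also leaves the repair of a Stage 1 compartment, alongside the main one, to the surgeon's judgement.

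No readable text restricts the two-stage branch or plans an analysis based on Stage 0 or 1 alone. The opening of 14.2 is redacted and the content of Table 3 is not shown, so such an analysis may exist out of sight.

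**The concern.** The first branch of Cured describes an anatomic end state. The second describes only an amount of change, and the two are joined by 'or'. A compartment can therefore be called cured at a stage that the study's own entry rules treat as prolapse. An Improved category already exists and would describe that result accurately.

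Cured is the best of the three primary outcomes. The study has a single arm, so no concurrent control is classified under the same rule, and 14.2 plans to set the results against published results for competing products. A more generous cure definition moves the estimate in one direction only, and a confidence interval does not show it. Any effect falls entirely on compartments with the most advanced baseline prolapse.

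**Working it through.** **Inputs.** The three definitions and compartment-level assessment come from 5.1, the eligible baselines from 6.3 and 6.4, and the 60 to 85 evaluable women at month 12 from 14.1. The POP-Q range 0 to 4 is assumed. The plan states no cure rate or baseline stage mix, so it offers no figure for this point to reproduce. Its evaluable numbers imply a loss of 1 - 60/70 = 14.3% to 1 - 85/100 = 15.0%, and nothing below depends on that.

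**Step 1: classify every transition under 5.1.**

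| Baseline stage | 1 yr: 0 | 1 yr: 1 | 1 yr: 2 | 1 yr: 3 | 1 yr: 4 |
|---|---|---|---|---|---|
| 2 | Cured | Cured | Failed | Failed | Failed |
| 3 | Cured | Cured | Improved | Failed | Failed |
| 4 | Cured | Cured | **Cured** | Improved | Failed |
| 1 (concurrent repair) | Cured | Failed | Failed | Failed | Failed |

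A two-stage gain from baseline 2 ends at 0, and from baseline 3 at 1. Both already satisfy the first branch. Only 4 to 2 is Cured through the second branch alone. Reading that branch as 'at least 2' changes nothing, because a gain of three or four stages also ends at 0 or 1.

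**Step 2: size.** Let s be the share of compartments at baseline Stage 4 and q the share of those at Stage 2 at one year. The cure proportion is raised by s x q. Both inputs are assumptions. Results in percentage points:

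| s | q = 10% | q = 25% | q = 50% |
|---|---|---|---|
| 2% | 0.2 | 0.5 | 1.0 |
| 5% | 0.5 | 1.25 | 2.5 |
| 10% | 1.0 | 2.5 | 5.0 |
| 20% | 2.0 | 5.0 | 10.0 |

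With one compartment per woman, the low corner is 60 x 0.002 = 0.12 to 85 x 0.002 = 0.17 compartments. The high corner is 60 x 0.10 = 6 to 85 x 0.10 = 8.5. Within the Stage 4 subgroup s = 1, so the rise is q itself: 10 to 50 points.

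**Step 3: scale.** The 95% half-width is 1.96 x sqrt(p(1 - p)/n). At an assumed cure rate of p = 0.8 it is 1.96 x sqrt(0.16/60) = 10.1 points for n = 60 and 1.96 x sqrt(0.16/85) = 8.5 points for n = 85. Most of the assumed range lies well inside this.

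**Step 4: test the remedy.** If the second branch is simply deleted, 4 to 2 has no category, because Improved covers a one-stage gain only. Improved must therefore be widened to at least one stage. If Cured is reworded as a bare Stage 0 or 1, a repaired Stage 1 compartment that stays at Stage 1 becomes both Cured and Failed. Keeping 'reduced to' avoids this. With both edits, every cell in the table has exactly one category, only 4 to 2 moves (Cured to Improved), and Cured plus Improved is unchanged.

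**The case against.** The definition is prespecified and open, and the endpoint is by design improvement from baseline. Some dependence on baseline is therefore intended. It also survives the fix: one-year Stage 2 would still be Failed from baseline 2 and Improved from baseline 3 or 4. That stands, and removing baseline dependence is not what the change achieves.

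A reader might infer that the plan calls cured a woman who would qualify for the study again. The documents do not support this. Entry requires Stage 2 or higher and also prolapse that needs surgery, and Section 2 says that many women need no treatment, depending on severity and stage. A residual Stage 2 meets the stage part only.

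A reader might also infer that the study's main result is materially inflated. The documents do not show this either. The primary outcome has three categories, the readable text does not single out the cure rate, and the frequency of the 4 to 2 transition is unknown and probably low. There is no predefined hypothesis, so no test or sample size rests on this cell. No information is lost, because POP-Q grading at baseline and one year lets Stage 0 or 1 be tabulated at any time.

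These arguments limit the size of the point. They do not make Stage 4 to Stage 2 a cure in the sense of the first branch.

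**Conclusion.** The point holds in a limited form. Given POP-Q stages 0 to 4, the two-stage branch does one thing: it labels Stage 4 to Stage 2 as cured, although the compartment is still at the stage threshold that the entry criteria use for prolapse. The overall effect is s x q, about 0.2 to 10 points under the assumed ranges and probably towards the lower part. Within Stage 4 compartments it is the whole share ending at Stage 2. The precision-based sample size is not affected. This is a cheap improvement to the meaning of the primary category and does not undermine the study.

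**What to change.** Make two edits in 5.1:

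1. End the Cured definition after its first branch, dropping the two-stage alternative and keeping the words 'reduced to'. A repaired Stage 1 compartment that stays at Stage 1 then remains Failed only.
2. In Improved, change a gain of one stage to a gain of at least one stage, so that Stage 4 to Stage 2 falls there.

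Leave Failed as it is. In 14.2, report the present Cured definition as a sensitivity analysis and tabulate the one-year outcome by baseline stage, so that any remaining dependence on baseline is visible.

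The cost is two wording changes and one extra table, with no new data. The reported cure rate may be slightly lower, and the cured-plus-improved rate stays the same.
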